Appendix 5: Definitions of Diagnostic Test Results

TEST RESULT	DESCRIPTION
Smear-positive	≥ 1 positive FM smear (inclusive of scanty positive smears) using WHO/IUATLD grading.
Culture-positive	LJ and/or MGIT culture growth-confirmed MTB complex.
Culture-negative	LJ or MGIT have no culture growth after >56 days and >42 days
Contaminated culture	LJ: Culture completely overgrown by bacterial or fungal contaminations within 3 weeks (discarded). In case of mixed cultures, isolated MTB colonies transferred to new LJ tube (repeat culture).
NGS INH-sensitive	Targeted NGS of katG , fabG1 , ahpC and inhA does NOT detect any mutations associated with INH resistance.
NGS INH-resistant	Targeted NGS of katG , fabG1 , ahpC and inhA detects at least one mutation associated with INH resistance.
NGS ETH-sensitive	Targeted NGS of inhA does NOT detect any mutations associated with INH resistance.
NGS ETH-resistant	Targeted NGS of inhA detects at least one mutation associated with INH resistance.
NGS FQ-sensitive	Targeted NGS of gyrA and gyrB does NOT detect any mutations associated with FQ resistance.
NGS FQ-resistant	Targeted NGS of gyrA and gyrB detects at least one mutation associated with FQ resistance.
NGS AMK-sensitive	Targeted NGS of rrs does NOT detect any mutations associated with AMK resistance.
NGS AMK-resistant	Targeted NGS of rrs detects at least one mutation associated with AMK resistance.
NGS KAN-sensitive	Targeted NGS of rrs and eis does NOT detect any mutations associated with KAN resistance.
NGS KAN-resistant	Targeted NGS of rrs and eis detects at least one mutation associated with KAN resistance.
NGS CAP-sensitive	Targeted NGS of rrs does NOT detect any mutations associated with CAP resistance.
NGS CAP-resistant	Targeted NGS of rrs detects at least one mutation associated with CAP resistance.
MTBDR _{plus} INH-sensitive	No detection of katG or inhA mutations associated with INH resistance by line probe assay (WT probe hybridization, no MUT probes hybridized).
MTBDR _{plus} INH-resistant	Detection of katG or inhA mutations associated with INH resistance by line probe assay (MUT probe hybridization or absence of WT probe hybridization).

MTBDRs/ FQ-sensitive	No detection of gyrA or gyrB mutations associated with FQ resistance by line probe assay (WT probe hybridization, no MUT probes hybridized).
MTBDRs/ FQ-resistant	Detection of gyrA or gyrB mutations associated with FQ resistance by line probe assay (MUT probe hybridization or absence of WT probe hybridization).
MTBDRs/ AMK-sensitive	No detection of rrs mutations associated with AMK resistance by line probe assay (WT probe hybridization, no MUT probes hybridized).
MTBDRs/ AMK-resistant	Detection of rrs mutations associated with AMK resistance by line probe assay (MUT probe hybridization or absence of WT probe hybridization).
MTBDRs/ KAN-sensitive	No detection of rrs or eis mutations associated with KAN resistance by line probe assay (WT probe hybridization, no MUT probes hybridized).
MTBDRs/ KAN-resistant	Detection of rrs or eis mutations associated with KAN resistance by line probe assay (MUT probe hybridization or absence of WT probe hybridization).
MTBDRs/ CAP-sensitive	No detection of rrs mutations associated with CAP resistance by line probe assay (WT probe hybridization, no MUT probes hybridized).
MTBDRs/ CAP-resistant	Detection of rrs mutations associated with CAP resistance by line probe assay (MUT probe hybridization or absence of WT probe hybridization).
Xpert MTB/XDR Drug*-sensitive	Valid result with Drug* resistance NOT detected by Xpert MTB/XDR.
Xpert MTB/XDR Drug*-resistant	Valid result with Drug* resistance detected by Xpert MTB/XDR.
Xpert MTB/XDR Drug*-indeterminant	Valid result with Drug* resistance indeterminant.
Xpert MTB/XDR non-determinant**	No valid run result by Xpert MTB/XDR.

* Drug: INH, ETH, FQ (moxifloxacin and levofloxacin for phenotypic DST), AMK, KAN or CAP

**Xpert non-determinants: result during initial run or after repeat following an invalid result

This document describes the statistical analysis plan for the following project: “Phase II: Multicentre Clinical Study to Assess the Performance of the Xpert MTB/XDR Assay for INH- and Second-line Resistance Detection”, Version 1.1, date: February 5th 2019.

1.1 Description of the study

In recent years, tuberculosis (TB) control efforts have been complicated by the rise and spread of MDR-TB, or TB that is resistant to the first-line drugs isoniazid (INH) and rifampicin (RIF), and XDR-TB, or MDR-TB that has developed additional resistance to a fluoroquinolone and any of the injectable compounds [amikacin (AMK), kanamycin (KAN) and/or capreomycin (CAP)]. The rapid diagnosis and appropriate treatment of M/XDR-TB is essential to prevent significant morbidity, mortality and further transmission of disease. For treatment of uncomplicated MDR-TB, the World Health Organization (WHO) recently endorsed a 6-9 month treatment regimen, thereby replacing conventional 18-24 month regimens. The fluoroquinolones and second-line injectables are key components of the 6-9 month regimen, and so it is necessary to rule-out resistance to these compounds prior to treating patients with the shorter regimen.

The Xpert MTB/RIF assay (Cepheid, Sunnyvale, CA) is an integrated, automated, cartridge-based system for MDR-TB diagnosis that uses the GeneXpert instrument platform. WHO confirmed evidence to support the widespread use of the Xpert MTB/RIF assay in 2010 and the assay has since been widely used in TB programs, but it is only capable of identifying *Mycobacterium tuberculosis* (Mtb) and detecting RIF resistance, and so it does not provide the comprehensive resistance profile necessary to determine if the shorter TB treatment regimen is appropriate for certain patients. Conventional diagnosis of TB drug resistance relies upon the slow growth of Mtb in solid or liquid media, only then followed by resistance testing to determine phenotypic drug resistance. These conventional drug susceptibility testing (DST) methods can take several weeks to yield results, require significant laboratory infrastructure and training, and are potentially biohazardous. In view of the inadequacy of these conventional tests for resistance detection, the development of rapid tests for INH and second-line resistance detection has become a research and implementation priority.

Rapid diagnostics for second-line drug resistance detection identify mutations in the *gyrA* and *gyrB* genes, associated with fluoroquinolone resistance, and *rrs* and *eis* gene regions, associated with second-line injectable resistance (with *eis* promoter mutations exclusively associated with KAN resistance).

Recently, a novel GeneXpert cartridge was developed to detect mutations occurring in these genes, as well as in the *katG* and *inhA* gene regions, associated with INH resistance. A Research Use Only (RUO) version of the Xpert MTB/XDR cartridge showed promising performance for INH and second-line resistance detection in a clinical evaluation study (sensitivity 92.7-98.1%; specificity 94.3-99.6%). The assay

chemistry has since been improved and additional gene targets have been added to the assay to improve the detection of INH resistance (i.e. fabG1 and ahpC). Evidence of assay accuracy from an external laboratory validation using a well-characterized set of Mtb strains as well as from large-scale, multicentre clinical studies is needed to confirm the validity of the most recent Xpert MTB/XDR assay for INH and second-line resistance detection, and to recommend its use in diverse clinical settings. The focus of this trial is the multicentre clinical evaluation.

The primary objectives of the trial are the following:

- 1.1 Estimate the diagnostic accuracy of the Xpert MTB/XDR assay for INH and ETH resistance detection
- 1.2 Estimate the diagnostic accuracy of the Xpert MTB/XDR assay for fluoroquinolone (FQ) resistance detection
- 1.3 Estimate the diagnostic accuracy of the Xpert MTB/XDR assay for second-line injectable resistance detection
- 1.4 Assess Xpert MTB/XDR technical performance, including non-determinant rates, ease of use and other systems operational characteristics.

The secondary objectives of the trial are the following:

- 2.1 Assess additional Xpert MTB/XDR performance characteristics, including direct performance versus performance on cultured samples, performance between sites, by smear result, by gene target and compared to Hain MTBDRplus and MTBDRsl

This is a multicentre, cross-sectional diagnostic accuracy trial, performed at clinical sites with high rates of drug-resistant TB in India, Moldova and South Africa. The expected duration of the trial is 10 weeks for IVD testing, with an additional 15 weeks to complete culture, DST, and NGS.

1.2 Timing of the analysis

The final analysis will be conducted once all results are available (i.e. patient enrolment is complete and all phenotypic DST and genotypic testing results have been returned). All objectives will be analysed together at this time.

2 Statistical hypotheses and methods

2.1 Primary outcome(s)

The primary outcomes of the study are the following:

- 1.1. Sensitivity and specificity estimates for INH and ETH resistance detection
- 1.2. Sensitivity and specificity estimates for fluoroquinolone resistance detection
- 1.3. Sensitivity and specificity estimates for second-line injectable resistance detection
- 1.4. Assessment of Xpert MTB/XDR operational aspects and ease of use

2.2 Secondary outcomes

The secondary outcomes of the study are the estimates of the following:

- 2.1. Assessment of additional Xpert MTB/XDR performance characteristics

3 Trial population and analysis datasets

3.1 Criteria for eligibility, recruitment, withdrawal and follow-up

Patients meeting the following criteria will be screened by Xpert MTB/RIF or Xpert MTB/RIF Ultra:

- Age 18 years or above;
- Symptoms suggesting pulmonary TB, i.e. persistent cough (generally ≥ 3 weeks or as per local definition of TB suspect), **and** at least one of the following:
 - Previously received >1 month of treatment for a prior TB episode **or**
 - Failing TB treatment with positive sputum smear or culture after ≥ 3 months of a standard TB treatment **or**
 - Had close contact with a known drug-resistant TB case **or**
 - Newly diagnosed with MDR-TB within the last 30 days **or**
 - Previously diagnosed with MDR-TB and failed TB treatment with positive sputum smear or culture after ≥ 3 months of a standard MDR-TB treatment regimen

Patients meeting the above criteria will be screened by Xpert MTB/RIF or Xpert MTB/RIF Ultra. TB patients meeting the following criteria will be included in the study:

- A clear Mtb-positive and RIF-resistant or RIF-sensitive result by Xpert MTB/RIF or Xpert MTB/RIF Ultra
- Provision of informed consent;
- Production of an adequate quantity (≥ 3 mL) of sputum

Participants will be excluded from the study if informed consent is not provided. For additional details, see section 4 of the trial protocol.

3.2 Analysis datasets

Describe the datasets that will be used in the analysis, like the examples below.

- ITT (Intention-To-Test) all subjects successfully enrolled in the study

- MITT (Modified-Intention-To-Test) all subjects in ITT for whom at least one test result is available, but not all (e.g. composite reference missing)
- PP (Per-Protocol) all subjects in ITT for whom results for all tests (Xpert MDR/XDR and composite reference standards) are available (complying with the protocol)
- QUEST (Questionnaire evaluation) all personnel who provided valid responses to the Xpert MTB/XDR Clinical Study User Appraisal Questionnaire

Samples meeting any of the following criteria in the course of the study will be excluded from the primary analyses of Xpert MTB/XDR accuracy:

- no valid result for NGS for relevant gene region or Xpert MTB/XDR,
- smear-positive/culture negative,
- single positive culture with ≤ 20 colonies (LJ) or time to positivity > 28 days (MGIT),
- culture positive but no MTB complex identification available,
- specimens with growth of mycobacteria other than MTB complex only

4 Description of statistical methods

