9.2 Statistical Analysis Plan

The statistical analysis plan (SAP) will be developed and finalized before database lock and will describe the samples to be included in the analyses and procedures for accounting for missing, unused, and spurious data. This section is a summary of the planned statistical analyses of the primary and secondary endpoints.

Primary analyses of outcome data will be done using the composite reference standard. Primary analyses will be focused on estimating accuracy (clinical sensitivity and specificity) for INH and second-line drug resistance detection:

- **Clinical Sensitivity:** proportion positive by composite reference standard (phenotypic DST and NGS) that are detected as positive by index test (Xpert MTB/XDR)
- **Clinical Specificity:** proportion negative by composite reference standard (phenotypic DST and NGS) that are detected as negative by index test (Xpert MTB/XDR)

For simple proportions (sensitivity and specificity), 95% confidence intervals will be computed using the Wilson score method. Primary diagnostic accuracy analyses will be carried out across all study sites. All TB samples that generate both Xpert MTB/XDR and composite reference standard results will contribute to the analysis of the performance characteristics for INH- and second-line resistance detection. If discordances are observed between the Xpert MTB/XDR results from testing sputa and the culture isolate, results from the culture isolate will be considered in these analyses.

Primary analyses will also evaluate assay operational characteristics, which will be captured through direct observation and user-appraisal questionnaires. Primary assessments of Xpert MTB/XDR operational characteristics will evaluate assay characteristics compared to Hain MTBDR*plus/sl* assays, including:

- Time to first result
- Ease of use
- Failure and invalid rate

These assessments of Xpert and LPA characteristics will be descriptive, and any differences will be further explored by sample type (i.e. smear- and culture-result, patient HIV- and treatment statuses, etc.). Assessments of platform operational characteristics will be based upon information gathered during the clinical study, as well as information provided by the manufacturers.

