9.2.1 Exclusion Criteria for Diagnostic Performance Analysis

Samples meeting any of the following criteria in the course of the study will be excluded from the primary analyses of Xpert MTB/XDR accuracy:

- no valid result for NGS for relevant gene region or Xpert MTB/XDR,
- smear-positive/culture negative,
- single positive culture with ≤ 20 colonies (LJ) or time to positivity > 28 days (MGIT),
- culture positive but no MTB complex identification available,
- specimens with growth of mycobacteria other than MTB complex only

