4.2 Analysis of the primary outcome(s)

The primary objectives 1.1, 1.2 and 1.3 will be analysed with the methodology described in section 4.1.

Outcome 1.1

Estimates of sensitivity and specificity of Xpert MTB/XDR will be calculated, for INH and ETH resistance detection with phenotypic DST and *katG*, *fabG1*, *ahpC* and *inhA* sequencing results as a composite reference standard (see Appendix). This outcome will be evaluated on the PP population.

Outcome 1.2

Estimates of sensitivity and specificity of Xpert MTB/XDR will be calculated, for fluoroquinolone resistance detection, with phenotypic DST and *gyrA* and *gyrB* sequencing results as a composite reference standard (see Appendix). This outcome will be evaluated on the PP population.

Outcome 1.3

Estimates of sensitivity and specificity of Xpert MTB/XDR will be calculated, for second-line injectable resistance detection, with phenotypic DST and *rrs* and *eis* sequencing results as a composite reference standard (see Appendix). This outcome will be evaluated on the PP population.

Outcome 1.4

Assess Xpert MTB/XDR operational aspects and ease of use, including Xpert MTB/XDR non-determinant rates.

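### The SAP's single per-protocol set, read literally, lets one drug's missing reference result remove a sample from every drug's primary analysis, against the drug-specific exclusion rule beside it

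*SAP*

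**What the plan says.** SAP 3.2 defines the PP set as "all subjects in ITT for whom results for all tests (Xpert MDR/XDR and composite reference standards) are available". The unit is the subject, and the reference standards are in the plural. The modified intention-to-test set in the same list takes enrolled subjects who have some results but not all, with a missing composite reference as its example. The list still stands under a line of template instruction: "Describe the datasets that will be used in the analysis, like the examples below".

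For each of outcomes 1.1 (INH and ETH), 1.2 (fluoroquinolones) and 1.3 (second-line injectables), SAP 4.2 states: "This outcome will be evaluated on the PP population".

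Three other rules bear on who is analysed:

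- Below the dataset list, SAP 3.2 repeats the exclusion criteria of Protocol 9.2.1. The first is "no valid result for NGS for relevant gene region or Xpert MTB/XDR". For sequencing, that is judged by the gene region that matters for the drug in question.
- Protocol 9.2 gives the inclusion rule: "All TB samples that generate both Xpert MTB/XDR and composite reference standard results will contribute to the analysis of the performance characteristics". It does not ask for results on all drugs.
- Protocol Appendix 5 defines a drug-level indeterminate Xpert MTB/XDR result as "Valid result with Drug* resistance indeterminant", and a non-determinant as "No valid run result by Xpert MTB/XDR".

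**The concern.** The trial reports separate accuracy estimates for INH, ETH, fluoroquinolones (FQ), AMK, KAN and CAP. A complete-case set formed once across all of them makes each estimate depend on the success of tests for the other drugs. An INH result with a sound INH reference would be discarded because a KAN test failed.

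Two things are at stake. The first is reproducibility: two analysts following the SAP in good faith could form different primary denominators, one by the PP definition and one by the drug-specific exclusion list. The second is precision, which is poorest for AMK and CAP, where only 34 resistant samples are planned.

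**Working it through.** **Step 1. The rules applied to two samples.**

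*Sample A: everything valid except the KAN susceptibility test.* It has no complete KAN composite result, so under the literal PP definition it is out for all six drugs. The exclusion list does not mention missing phenotypic testing, so it neither removes this sample nor can it restore one that never entered PP. Under Protocol 9.2 the sample contributes to INH, ETH, FQ, AMK and CAP.

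*Sample B: everything valid except sequencing of* eis. Under literal PP it is again out for all six. Under the exclusion list it is out only where *eis* is a relevant region: KAN by Protocol Table 1, and also AMK if SAP Table 4 is followed, since that table lists *eis* for AMK too.

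The rules give different answers for both samples, and the tension lies inside SAP 3.2 as well as between SAP and protocol.

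**Step 2. The plan's own figures (Protocol 9.1 and Appendix 4; SAP 10).**

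- Analysable samples: 360 × 0.79 = 284.4, taken as 284; 400 × 0.79 = 316; total 600. Conversely, 600 / 0.79 = 759.5, i.e. 760 tested.
- AMK/CAP-resistant: 284 × 0.02 = 5.7 and 316 × 0.09 = 28.4, i.e. 6 + 28 = 34.
- FQ-resistant: 284 × 0.05 = 14.2 and 316 × 0.25 = 79, i.e. 14 + 79 = 93.
- Interval: Wilson score with continuity correction, z = 1.96, p = 0.90.
  - Lower = [2np + z² − 1 − z√(z² − 2 − 1/n + 4p(n(1−p) + 1))] / [2(n + z²)]
  - Upper = [2np + z² + 1 + z√(z² + 2 − 1/n + 4p(n(1−p) − 1))] / [2(n + z²)]
  - n = 34: (64.04 − 8.23)/75.68 = 73.7% and (66.04 + 7.45)/75.68 = 97.1%, width 23.4 points (Table 2: 23%).
  - n = 93: 81.6% to 95.0%, width 13.4 points (Table 2: 13%).

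Table 2 is reproduced. Its counts add to 600 for every drug (395 + 205, 93 + 507, 34 + 566, 71 + 529). That fits a complete-case set, or a plan that assumed no drug-specific loss, so it does not settle which rule is meant.

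**Step 3. Literal rule against per-drug rule.** The documents give no per-drug missing rate, so m is an assumption. With losses independent over six drug results:

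- literal rule: N = 600 × (1 − m)⁶
- per-drug rule: N = 600 × (1 − m)

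The same factors are applied to the resistant counts. Each cell gives literal vs per-drug.

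| m | N | Difference in N | AMK/CAP-resistant n | CI width (points) | Extra width |
|---|---|---|---|---|---|
| 1% | 565 vs 594 | 29 | 32 vs 34 | 24.2 vs 23.4 | 0.8 |
| 2% | 532 vs 588 | 56 | 30 vs 33 | 25.1 vs 23.8 | 1.3 |
| 3% | 500 vs 582 | 82 | 28 vs 33 | 26.0 vs 23.8 | 2.2 |

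Extra width is the difference of the rounded widths. For FQ the resistant n is 88 vs 92, 82 vs 91 and 77 vs 90, with widths of 13.8 vs 13.5, 14.3 vs 13.6 and 14.9 vs 13.6 points.

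The per-drug rule is the right comparator because it too loses samples. If failures clustered completely in the same samples, the two rules would give the same N and the gap would be zero.

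**The case against.** The strongest reply is that the SAP already contains the drug-specific rule. The sequencing exclusion directly below the PP definition refers to the relevant gene region, and SAP 4.2 names each outcome's own genes and composite standard before applying PP. The plural could then be read outcome by outcome. This stands in part: deletion across all drugs is the literal reading, not the only one, and the SAP does not simply depart from the protocol, since it carries the same exclusion list. It does not remove the problem. An exclusion criterion can only take samples out, its drug-specific wording covers sequencing and not a missing susceptibility test, and the modified intention-to-test line points to the strict reading.

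On size, the objection is largely right. Six independent failures is an extreme case: AMK, KAN and CAP share *rrs*, INH and ETH share *inhA*, and the reference tests share one isolate. Some of the assumed loss may also sit within the 10% molecular non-determinant allowance in Appendix 4, although that allowance does not name failure of a single drug's susceptibility test.

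A reader might infer two further things that the documents do not support:

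- *That an indeterminate Xpert result for one drug also removes the sample everywhere.* Appendix 5 classes it as a valid result, and PP asks only that results be available. What can be said is that such a result fits no cell of the two-by-two table in SAP 4.1, and neither document says how to count it.
- *That the lost samples are mainly of low bacillary load, so that accuracy is biased upwards.* Susceptibility testing and sequencing are done on the culture isolate (Protocol 6.1.2 and 7.1), so sputum load is not the evident cause of a missing reference result.

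**Conclusion.** The point holds as a conflict over the primary denominator. Followed to the letter, SAP 3.2 with 4.2 removes a sample from every drug's primary analysis when one drug's reference result is missing. The drug-specific exclusion and Protocol 9.2 imply otherwise, and the leftover template line suggests that the question was never settled.

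The cost in precision is modest: at an assumed 1% to 3% loss per drug, independent over six drugs, 29 to 82 of 600 samples more than a per-drug rule would lose, and about 0.8 to 2.2 points on an AMK/CAP interval already some 23 points wide. These are upper-end figures resting on an assumed rate, and clustering would shrink them. The direction and size of any bias are unknown. The change is still worth making, because the literal rule discards usable data and leaves the primary analysis set open to choice.

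**What to change.** Before database lock, replace the template line and the PP entry in SAP 3.2 with a definition by drug: *for each drug, all ITT subjects with a resistant or sensitive Xpert MTB/XDR result and a composite reference result for that drug, meeting no exclusion criterion*. Asking only for a valid Xpert result would not be enough, because Appendix 5 counts an indeterminate as valid.

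Report, for each drug, the n analysed and the number of drug-indeterminate Xpert results. If wanted, keep the set complete for all drugs as a sensitivity analysis.

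The cost is one or two sentences in the SAP and no new data. Denominators will differ between drugs, so the tables must show n for each.
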